### 7.5 Criteria for Premature Discontinuation of Investigational Medicinal Product Administration

There are circumstances under which receipt of a further trial vaccine dose is a contraindication in this trial. These circumstances include anaphylaxis or severe hypersensitivity reactions following the initial vaccination. If these reactions occur, the subject must not receive additional trial vaccine but the subject's LAR is encouraged to allow the child to continue in trial participation for safety follow-up and efficacy and immunogenicity data collection.

Early termination of a subject's trial participation will by default prevent the subject from receiving further doses of investigational vaccine, as the subject will no longer be participating in the trial. In addition to criteria for early termination of a subject's participation (see Section 7.4), other situations may apply in which subjects may continue participating in the trial (e.g.,

HIL-214	
Trial No. NOR-212	Page 53 of 100
Protocol DOC-00351, 3.0	1 September 2023

contributing safety and other data according to protocol) but investigational vaccine administration is discontinued. Even if the subject is deemed ineligible to receive further doses of trial vaccine, all efforts should be made to continue the collection of data according to protocol.

In addition, the primary reason for premature discontinuation of trial vaccine administration should be recorded in the (electronic) case report form (eCRF, end of trial vaccine administration page) using the following categories:

- 1. Adverse Event: The subject has experienced an AE (irrespective of being related/unrelated to the trial vaccine or trial-related procedures) for which subsequent trial vaccine administration(s) pose an unacceptable risk to the subject's health, but the subject will continue trial participation for safety, or for a subset of other trial procedures.
- 2. Lost to follow-up: The subject did not return to the curic and at least three attempts to contact the subject were unsuccessful.
- 3. Withdrawal of consent: The subject's LAR wishes to withdraw the child from the trial. The primary reason for early termination will be with lrawal of consent if the subject's LAR withdraws the child from participation due to a not-medical reason (i.e., reason other than an AE). The reason for withdrawal, if provided, should be recorded in the eCRF.
- 4. **Premature trial termination** by sporter, regulatory agency, the IEC/IRB, or any other authority.

If the clinical trial is prematurely terminated by the sponsor, the investigator is to promptly inform the trial subjects and local IEC/IRB and should assure appropriate follow up for the subjects. The primary reason for early termination in this case will be trial termination.

- 5. Subject's **death** prior to react trial vaccine administration.
- 6. **Protocol deviation**: A protocol deviation is any change, divergence, or departure from the trial design or procedures of a trial protocol. The subject may remain in the trial unless continuation in the trial jeopardizes the subject's health, safety or rights (see Section 7.4).
- 7. Other reason for early termination that is not captured by the above prespecified categories.

For criteria which also lead to early termination of a subject's trial participation, please refer to Section 7.4.

### 8.0 CLINICAL TRIAL MATERIAL MANAGEMENT

This section contains information regarding all investigational vaccines, placebo, and materials provided directly by the sponsor, and/or sourced by other means, that are required by the trial protocol, including important sections describing the management of clinical trial materials (CTM).

### 8.1 Investigational Products

Descriptions for the investigational vaccine and the placebo are provided in the following sections.

### 8.1.1 Investigational Vaccine

HIL-214 for injection is provided by HilleVax, Inc. in single dose 1 mL pre-filled syringes as a 0.65 mL volume (to deliver a 0.5 mL dose). The investigation of vaccine contains 50 µg GI.1/150 µg GII.4c VLPs and 500 µg of aluminum at ALOH)3.

The syringe contents may appear biphasic with a clear upper layer and a white precipitate. After mixing by shaking, a uniformly turbid systemsion should be observed.

Each HIL-214 pre-filled syringe with be structed in a tamper-evident, single dose carton.

### 8.1.2 Placebo

Placebo [0.9% sodium chloride (saline)] for injection is provided by HilleVax, Inc. or designated vendor, in a container allowing delivery of a 0.5 mL dose). The placebo does not contain any preservatives.

The contents of the placebo container will appear clear and therefore, distinguishable from the vaccine.

Each placebo container will be supplied in a tamper-evident, single dose carton.

### 8.2 Labeling

A clinical label will be affixed to trial vaccine containers in accordance with local regulatory requirements.

### 8.3 Inventory and Storage

Vaccines will be shipped in refrigerated, temperature-controlled containers with a temperature monitor. The trial vaccine must be stored, kept away from light, and maintained at a controlled temperature of 2°C to 8°C (36°F to 46°F), as specified on the label. The trial vaccine must be kept in an appropriate, limited access, secure place until it is used or returned to the sponsor or

HIL-214	
Trial No. NOR-212	Page 55 of 100
Protocol DOC-00351, 3.0	1 September 2023

designee for destruction. The trial vaccine must not be frozen. Each kit is intended for single use only.

Receipt and dispensing of trial vaccine must be recorded by authorized personnel at the trial site. All sponsor-supplied trial vaccine and placebo must be stored under the conditions specified on the label, and remain in the original container until dispensed. A daily temperature log of the vaccine storage area must be maintained every day. Temperature excursions must be reported to the sponsor as soon as possible and use of these vaccines requires sponsor approval. Temperature excursion information can be found in the Pharmacy Manual.

### 8.4 Dose and Regimen

The trial vaccine dose of 50  $\mu$ g GI.1/150  $\mu$ g GII.4c VLPs and 500  $\mu$ g of aluminum as Al(OH)3 or placebo will be administered intramuscularly at Visit 1 (Tay 1) and Visit 2 (28 to 56 days after the first dose) in the anterolateral thigh muscle.

### 8.5 Investigational Medicinal Product Assignment and Dispensing Procedures

The vaccine identification number of the kit to be addinistered will be assigned by the IRT.

The vaccine and placebo are visually distinguishable and therefore, to maintain the blind, the trial vaccine doses will be prepared and administered by the unblinded designee according to the instructions in the Pharmacy Manual

The investigator or designee will be esponded by the procedures stipulated in this trial protocol. All vaccines will be administered only by unblinded personnel who are qualified to perform that function under applicable laws and regulations for that specific trial.

Expired vaccines must not be dministered.

If sponsor-supplied kit is lost or damaged, the site can request a replacement from the IRT (refer to IRT manual supplied separately). At the subsequent dose-administration visit, the investigator or designee will again contact the IRT to request an additional kit for a subject.

# 8.5.1 Precautions to Be Observed When Administering the Investigational Medicinal Product

Prior to trial vaccine administration, a subject must be determined to be eligible to receive trial vaccine (Sections 7.1 and 7.2), and it must be clinically appropriate in the judgment of the investigator to administer the HIL-214 or placebo.

Prior to subsequent trial vaccine administration, site staff must determine if the subject is eligible to receive vaccination by evaluating the criteria outlined in Sections 7.3, 7.4 and 7.5.

Standard immunization practices are to be observed and care should be taken when administering a trial vaccine intramuscularly. In addition, World Health Organization (WHO) recommendations to reduce anxiety and pain at the time of vaccination should be followed [27].

HIL-214	
Trial No. NOR-212	Page 56 of 100
Protocol DOC-00351, 3.0	1 September 2023

Before administration of trial vaccine/placebo, the vaccination site must be disinfected with a skin disinfectant (e.g., 70% alcohol). Allow the skin to dry. Refer to the Pharmacy Manual for details on preparation and administration of trial vaccine.

As with all injectable vaccines, trained medical personnel and appropriate medical treatment should be readily available in case of anaphylactic reactions post vaccination. For example, epinephrine 1:1000, diphenhydramine, and/or other medications for treating anaphylaxis should be available.

### 8.6 Randomization Code Creation and Storage

The investigator or investigator's designee will access the IRT at Visit 1 (Day 1) to obtain the subject number.

The investigator or investigator's designee will utilize the IKT or randomize all subjects into either the HIL-214 or placebo arms. During this contact, the vestigator or designee will provide the necessary subject identifying information.

Randomization information will be stored in a securid area, accessible only by authorized personnel.

# 8.7 Investigational Medicinal Product Bling Maintenance

The blind will be maintained by the anbig ded designee.

This is a double-blind trial; the investor and subject's LAR are blinded to trial vaccine assignment. Trial vaccine identity label ext as HIL-214 or placebo) will be included on the trial vaccine container label.

# 8.8 Unblinding Procedu

The trial vaccine blind shall not be broken by the investigator unless information concerning the HIL-214 is necessary for the medical treatment of a subject. In the event of a medical emergency, if possible, the medical monitor should be contacted before the trial vaccine blind is broken to discuss the need for unblinding. For unblinding a subject, the trial vaccine blind can be obtained by the investigator, by accessing the IRT.

The sponsor's pharmacovigilance department must be notified as soon as possible if the trial vaccine blind is broken by the investigator and the completed SAE form, if applicable, must be sent within 24 hours. The date, time, and reason the blind is broken must be recorded in the source document and the same information (except the time) must be recorded on the eCRF.

If any subject is unblinded, the subject must be withdrawn from the trial and their data no longer evaluated. Subjects should continue to be monitored for safety follow-up.

HIL-214	
Trial No. NOR-212	Page 57 of 100
Protocol DOC-00351, 3.0	1 September 2023

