#### Safety analysis

In general, data imputation will not be performed for any missing safety data. All safety data summaries will be prepared using SAF.

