# 7.4 Criteria for Early Termination of a Subject's Trial Participation

Under some circumstances, a subject's trial participation may be terminated early. This means that no further trial procedures (including data collection) will be performed on that subject beyond the specific date of early termination of trial participation. The primary reason for early

HIL-214	
Trial No. NOR-212	Page 52 of 100
Protocol DOC-00351, 3.0	1 September 2023

termination of the subject's trial participation should be documented using the following categories.

For screen failure subjects, refer to Section 9.1.9.

- 1. Adverse Event: The subject has experienced an AE (irrespective of being related/unrelated to the trial vaccine or trial-related procedures) that requires early termination because continued participation imposes an unacceptable risk to the subject's health and/or the subject's LAR is unwilling to allow the child to continue participation because of the AE. If the subject's LAR is unwilling to allow the child to continue because of the AE, the primary reason for early termination of trial participation in this case will be withdrawal due to AE and not withdrawal of consent, see below.
- 2. Lost to follow-up: The subject did not return to the clipis and at least three attempts to contact the subject's LAR were unsuccessful.
- 3. Withdrawal of consent: The subject's LAR wishes to withdraw the child from the trial. The primary reason for early termination will be withdrawal of consent if the subject's LAR withdraws the child from participation due to a non-medical reason (i.e., reason other than AE). While the subject's LAR has no obligation to provide a reason for withdrawing consent, attempts should be made to determine the underlying reason for the withdrawal and, where possible, the primary underlying reason should be documented.
- 4. **Premature trial termination** by the pontor, a regulatory agency, the IEC/IRB, or any other authority.

If the clinical trial is prematurely terminated by the sponsor, the investigator is to promptly inform the subject's LAR and local IEC/IRB and should assure appropriate follow up for the subjects. The primary resen for early termination in this case will be trial termination.

- 5. Subject's **death** during trial articipation.
- 6. Other reason for early termination that is not captured by the above prespecified categories.

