## 10.4.4 Collection and Reporting of Serious Adverse Events

Collection of SAEs will commence from the time that the subject's LAR signs the ICF. Routine collection of SAEs will continue until the end of the trial (up to 2 years of age).

SAEs should be reported according to the following procedure:

A sponsor SAE form must be completed, in English, and signed by the investigator immediately or within 24 hours of first onset or notification of the event. The information should be completed as fully as possible but contain, at a minimum:

- A short description of the event and the reason the event is categorized as serious.
- Causality assessment.
- Protocol number.
- Subject identification number.
- Investigator's name.

The SAE form should be transmitted within 24 hours to

If the eCRF system is unavailable, a paper sponsor SAE form/paper CRF should be completed and the event must be entered into the eCRF once access to restored.

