## 13.0 STATISTICAL METHODS

## 13.1 Statistical and Analytical Plans

A statistical analysis plan (SAP) will be prepared and finalized prior to unblinding of subject's trial arm. This document will provide further details regarding the definition of analysis variables and analysis methodology to address all trial objectives.

A blinded data review will be conducted prior to unblinding of subject's assignment to a trial arm. This review will assess the accuracy and completeness of the trial, database and subject evaluability.

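### Protocol 8.8 stops evaluating an unblinded subject's data without limiting this to efficacy, which conflicts with the Safety Set analysis and is not overridden in the SAP

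*Protocol*

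**What the plan says.** Protocol 8.8 forbids the investigator to break the blind "unless information concerning the HIL-214 is necessary for the medical treatment of a subject". It then gives the consequence: "If any subject is unblinded, the subject must be withdrawn from the trial and their data no longer evaluated". The next sentence adds: "Subjects should continue to be monitored for safety follow-up". No data type and no analysis set is named.

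The analysis sections are inclusive. Protocol 13.1.1 and SAP 9.1.1 put every randomised subject with one or more doses in the Safety Set (SAF). The protocol synopsis states: "All safety data summaries will be prepared using SAF". SAP 12.0 repeats the SAF basis and, for the end-of-trial analysis, summarises SAEs from first dose to trial end. SAP 12.1.4 takes SAE percentages over the SAF. For efficacy, Protocol 13.1.3 and SAP 9.3.6.1 censor withdrawn subjects; they do not remove them.

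On early termination, Protocol 7.4 says that "no further trial procedures (including data collection) will be performed on that subject beyond the specific date of early termination".

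**The concern.** The clause in 8.8 is a rule about analysis placed in an operational section, and it covers all of a subject's data. If a programmer follows it, a subject who belongs to the SAF has later safety events left out of SAF tables. If the programmer follows the SAP, those events are counted. The two documents give different tables, and neither says which governs.

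The subjects concerned are not a random subset. A permitted code break requires that someone needed the treatment identity in order to treat the infant, so the exclusion would be triggered by a medical event after randomisation. A comparative safety summary should not lose data for that reason, however few the subjects.

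SAE reporting to the sponsor is not at stake, because Protocol 8.8 and 10.4.4 keep that route open. The question is whether the events enter the summaries.

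**Working it through.** **Step 1. Set 8.8 against the rest of the plan, by data type.**

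- *Safety.* SAF membership depends only on randomisation and one dose (Protocol 13.1.1, SAP 9.1.1). The SAP's single ground for removal is a major GCP violation, and a code break that 8.8 permits is not one. SAP 12.0 and 12.1.4 contain no exception for unblinded subjects. Under 8.8 the later data are not evaluated. This is a conflict.
- *Efficacy.* A subject withdrawn under 8.8 has discontinued the study. SAP 9.3.6.1 censors at the earliest of last contact, discontinuation and end of the primary observation period. Later efficacy time is therefore already outside the analysis, and the clause adds nothing.
- *Immunogenicity.* Results are summarised in the FAS and PPS-I (Protocol 13.1.4, SAP 11.6.1). Neither document says how results from an unblinded subject are handled.
- *Override.* SAP 6.1 lists three departures from the protocol: calendar day in place of a 24-hour period, concentration units, and PPS-I membership. None concerns 8.8. SAP 11.4 decides exclusions from PPS-E and PPS-I only, and its seven deviation categories do not name code breaks. Elsewhere the SAP mentions unblinding only at the level of the whole trial.

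**Step 2. Which safety data are exposed.**

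Solicited events are collected for 7 days and unsolicited events for 28 days after each dose (Protocol 10.4.1, 10.4.2). After those windows, mainly SAEs and adverse events leading to withdrawal remain. If safety collection runs to age 24 months, and ignoring the 14-day entry window either side of 5 months, the follow-up left after a code break is:

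- on the day of dose 1: 24 − 5 = 19 months;
- 28 days after a dose 2 given at 28 days: 24 − (5 + 56/30.4375) = 17.2 months;
- 28 days after a dose 2 given at 56 days: 24 − (5 + 84/30.4375) = 16.2 months.

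If 7.4 governs instead, nothing is collected after withdrawal, and the loss is one of collection, not analysis.

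**Step 3. How many infants, and what the table would lose.**

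The documents give no expected number of code breaks. Assumed rates of 0.1%, 0.5% and 1% give 3000 × 0.001 = 3, 3000 × 0.005 = 15 and 3000 × 0.01 = 30.

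Suppose k subjects in an arm of 1500 have an SAE only after unblinding, and those SAEs are left out while the subjects stay in the SAF denominator. The observed proportion falls by k/1500: 0.067% for k = 1, 0.200% for k = 3 and 0.333% for k = 5. An SAE term seen once, 1/1500 (Clopper-Pearson 95% CI 0.002% to 0.371%), becomes 0/1500 (upper limit 0.246%) and disappears from the table. These values of k are illustrations, not forecasts.

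**Step 4. Bound the effect on efficacy.**

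The plan claims more than 80% power with 24 cases at a true VE of 70%. By the Schoenfeld approximation, with D cases, 1:1 allocation, hazard ratio 0.3 and two-sided 5%:

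power = Φ(√(D/4) × |ln 0.3| − 1.96)

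- D = 24: Φ(2.449 × 1.204 − 1.96) = Φ(0.989) = 83.9%, consistent with the claim.
- D = 24 × 0.99 = 23.76: Φ(2.437 × 1.204 − 1.96) = Φ(0.974) = 83.5%.

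Losing 1% of cases outright, which is more than the clause does beyond existing censoring, costs 0.4 percentage points.

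**Step 5. Compare 7.4 with 8.8.**

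Section 7.4 ends all data collection at early termination. Section 8.8 withdraws the subject and keeps safety follow-up going. Both cannot apply to the same infant.

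**The case against.** The strongest reply is that the benign reading is the natural one. The sentence directly after the clause continues safety follow-up. Section 8.8 belongs to the chapter on trial materials, Protocol 13.1 leaves analysis detail to the SAP, and the SAP's set definitions and SAE summaries have no exception for unblinded subjects. A sensible analyst might keep the safety data and stop only efficacy. It can be added that the blinded data review settles such cases: "This review will assess the accuracy and completeness of the trial, database and subject evaluability".

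Much of this is fair, and it makes the point one of conflicting text, not demonstrated data loss. It does not resolve the conflict. The follow-up sentence is about monitoring an infant, and is compatible with data being collected and then not analysed. The SAP lists its departures from the protocol in 6.1 and does not list this one. The blinded review has no criterion for code breaks, and SAP 11.4 uses it only for the per-protocol sets.

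Four stronger inferences should be resisted:

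- *Retroactive removal.* A reader might infer that everything from an unblinded subject is erased, including the event that prompted the code break and any earlier efficacy case. The words *no longer* point forward in time, and the set definitions and censoring rule keep earlier data. The documents do not support erasure, so calculations in which a removed case reverses the efficacy result carry little weight.
- *Highest-risk infants.* It is tempting to say that unblinded infants are those most likely to have an SAE. Section 8.8 requires only that the information be needed for treatment and asks for an SAE form where applicable. No document gives their SAE risk.
- *Long loss of all safety data.* The 16 to 19 months in the working are not months of full adverse event collection, because the routine windows are short.
- *Conflict with 7.5.* That section says "all efforts should be made to continue the collection of data according to protocol", but for subjects who stop vaccination and remain in the trial. It does not contradict 8.8, which concerns subjects withdrawn.

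**Conclusion.** The point holds for safety data collected after an individual code break. Taken as written, 8.8 leaves those data unevaluated, against the SAF definition and the SAF-based summaries through trial end, and the SAP does not override it. The exclusion would be selected on a medical event after randomisation.

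Its size is probably small. The number of code breaks is not stated; the 3 to 30 infants rest on assumed rates, and how many would have an SAE afterwards is unknown. The effect would be seen mainly in rare SAE terms, where a single event decides whether the term appears. The effect on power and on the efficacy conclusion is negligible, because withdrawn subjects are already censored.

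Confidence is high that the texts conflict. Whether any data would in fact be lost depends on how the analyst reads them, and on whether 7.4 or 8.8 governs collection after withdrawal. It is worth correcting because the remedy costs almost nothing.

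**What to change.** Delete the data-evaluation clause from the quoted sentence of Protocol 8.8, or override it in SAP 6.1 or 9.1 before treatment codes are opened. The text should state that:

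1. individually unblinded subjects stay in every analysis set whose definition they meet (SAF and FAS after one dose, mFAS only after two);
2. all safety data collected before and after unblinding are summarised in the SAF;
3. efficacy events and person-time up to study discontinuation count, with censoring at the discontinuation date under SAP 9.3.6.1, which does not list unblinding itself as a censoring date;
4. immunogenicity results already collected stay in the FAS summaries, and PPS-E and PPS-I status is decided in the blinded review under SAP 11.4.

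Separately, Protocol 7.4 and 8.8 must be reconciled on data collection after withdrawal. Which conduct rule applies is for the sponsor to decide, and none is proposed here.

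The cost is one deleted clause in the protocol or a short SAP entry. No new data, analysis or change in sample size is needed.
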